9.3.2.2 Secondary outcomes

Secondary endpoint

- Health care utilization : Medical cost / number of annual visits, prescriptions and hospitalizations (hospitalization mainly due to severe exacerbation of COPD) over one year.
- All-cause mortality
- Recorded incidence of lung cancer (based on ICD-10 code C34.XX)

[REDACTED]

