9.5 STUDY SIZE

In 2008~2013 NHI database, approximately 200,000 patients per year with COPD were diagnosed using COPD diagnostic code and a prescription for COPD medications (LAMA, LABA, ICS + LABA, SAMA, SABA, SAMA + SABA, PDE-4, systemic beta agonist, theophylline). In COPD patients, the use of LAMA and ICS/LABA was 26 to 37%, respectively. We expect the study to include a minimum of 5,000 patients per arm, a conservative estimate.

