9.6 DATA MANAGEMENT

We will collect the data from the medical insurance claims from the Korean National Health Insurance (NHI) claims database, which will be provided for research purposes by the Korean NHIC with strict confidentiality guidelines All analyses were performed with SAS and R .

Data for this study will be obtained via the following sources:

- Eligibility DB
 - Sociodemo-graphics variables : sex, age, residential area, insurance type (the employee insured, the self-employed insured, dependants, medical aid), monthly contributions, occupation
 - Vital statistics : dates of birth and death, cause of death (ICD-10 codes)
- Health care utilization DB
 - Diagnosis : International Classification of Disease-10 codes (main disease code, sub disease code)
 - Utilization and cost : date of visit, types of medical institutions (clinics/hospitals/tertiary hospitals/public health centres), types of visit (inpatient/outpatient/emergency/intensive care), length of stay, medical cost (insurer/patient), et al.
 - Health care procedures and medications : Operation and procedure codes, medication history (generic name code, dose, duration of prescription), material codes, et al.

Data is extracted from the NHIS and stored on a secured, shared server for statistical analyses. The original data will be stored in its own, read-only directory to protect the integrity of the extracted data. After obtaining an approval from the NHIS, data analysts can access the data and conduct analysis in a secured computer. NHIS's policy strictly forbids exportation of the original data, however, results obtained from statistical analyses can be exported after an internal review.

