9.7.1.1 Propensity score methodology

The propensity score will model the likelihood among COPD patients of receiving LAMA and ICS/LABA. The model for the propensity score will to the extent possible include the following elements:

- 1) Age and sex
- 2) Socioeconomic status (e.g. income, educational level, single living)
- 3) History of COPD exacerbation
- 4) Charlson Comorbidity Index
- 5) History of asthma

A logistic regression analysis will be performed on the identified COPD patients where treatment with LAMA and ICS/LABA groups is the dependent, dichotomous variable and the independent variables are listed above (age, sex and history of COPD exacerbation et al.). Based on this analysis, the propensity score is calculated for each patient. For subgroup analyses, PS matching and evaluation of its success, as presented below, will be re-done as covariate balance is not automatically maintained in sub-cohorts.

Smoking may be an important confounder in COPD but smoking status is usually not available in the databases at all. If smoking status is confirmed to be available, the data will be analysed with and without smoking status included in the model and the magnitude of the confounding effect assessed (sensitivity analysis).

PS matching will be done in a 1:1 ratio using the nearest-neighbor algorithm, using calipers of width equal to 0.2 of the standard deviation of the logit of the PS (matches of the main exposure sub-cohort and the comparator sub-cohort are formed if the caliper width is not exceeded for the logit of PS). For LAMA-exposed patient to ICS/LABA-exposed patients will be selected within the same matching interval of the propensity score. The distribution of propensity scores will be examined between LAMA-exposed and eligible ICS/LABA-exposed. In the matching procedure, matched comparator sub-cohort patients (ICS/LABA) will be removed from the pool of eligible patients among the comparator sub-cohort so that a matched patient is no longer available for consideration as a potential match for another exposed patient.

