9.7.2 Main analysis

For the primary effectiveness outcomes incidence rates (events per 1,000patients-years) with corresponding 95% confidence intervals (CI) will be calculated. This will be evaluated by a matched Cox proportional hazards regression model for counting processes, which allow the follow-up time to be divided into several periods and therefore control for baseline and time-dependent covariates, using the full observational period of available data, i.e. up to 11 years of follow up. The Cox proportional hazards regression will take into account the fact that individual matching (1:1) will be performed by considering the exposed patient and his/her matched controls as one stratum and including this as a stratum in the Cox proportional hazards model. Additional variables will be included in the model if available. The cumulative incidence plots will be accompanied by number of patients at risk at different time points during follow-up. For (possibly) repeating events (such as exacerbation event) additionally a Poisson regression model will be fitted for the number of events (taking into account the matching). Time in the study will be included as an offset variable in the model. The cox and Poisson models will be adjusted for unbalanced PS-variables at baseline.

The outcome will be analyzed separately for each:

- 1) Primary outcome
 - Comparison of pneumonia incidence in COPD patients using LAMA and ICS/LABA
 - Comparison of exacerbations frequency and rate in COPD patients using LAMA and ICS/LABA : moderate or severe exacerbation

Proprietary confidential information © 2022 Boehringer Ingelheim International GmbH or one or more of its affiliated companies

[figure not shown]
- Comparison of time to start triple combination therapy (time from initial 'LAMA mono' or ICS+LABA' to 'LAMA+LABA+ICS' combination) in COPD patients using LAMA and ICS/LABA

2) Secondary outcome

- Comparison of all-cause mortality differences in COPD patients using LAMA and ICS/LABA
- Comparison of lung cancer incidence in COPD patients using LAMA and ICS/LABA
- Comparison of health care utilization: Medical cost / No. of prescriptions, visits and hospitalizations (hospitalization mainly due to severe exacerbation of COPD)

Health care utilization

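### Pre-index cost, visits and all-cause admissions are in no visible covariate list, so a baseline difference in them could go unseen and pass into the utilisation comparison

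*Combined protocol and SAP*

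**What the plan says.** Section 9.3.2.2 gives a secondary outcome of "Medical cost / number of annual visits, prescriptions and hospitalizations". Sections 8 and 9.7.2 present it as a comparison between the two treatments. The utilisation paragraph of 9.7.2 covers total expenditure as well as COPD-related use and cost. It works arm by arm and names no between-group model, baseline period or covariate.

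Section 9.7.1.1 lists five elements for the propensity score: age with sex, socioeconomic status, exacerbation history, Charlson index and asthma history. Of the logistic model it says that "the independent variables are listed above (age, sex and history of COPD exacerbation et al". Section 9.7.1 also matches on sex, age band and time since COPD diagnosis; 9.3.3 mentions income or insurance. Section 9.12 describes a somewhat wider score that takes in use of other drugs, but not cost, visits or admissions.

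On adjustment, 9.7.2 states: "The cox and Poisson models will be adjusted for unbalanced PS-variables at baseline". The trigger in 9.7.1.1 is a standardised difference above 0.1 in a propensity score variable. Two further clauses are open-ended: 9.7.1.1 permits extra adjustment in additional models, and 9.7.2 provides for more variables if they are available. Neither names a variable.

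The data are at hand. Section 9.6 lists visit dates, visit types and "length of stay, medical cost (insurer/patient), et al", and Appendix Table 1 lists expense, visit-day and inpatient-date fields.

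**The concern.** For a cost or visit outcome, the patient's own cost or visits before the index prescription are the natural baseline value. They usually predict later use, and they also mark severity in a source with little else to measure it: no lung-function variable appears in 9.6 or Appendix Table 1, and the comments in Annex 2 say that the claims do not show smoking status.

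If the arms differ on prior use after matching, part of that difference reappears in follow-up and would be reported as an effect of treatment. The stated safeguard would not necessarily show it. The rule that turns imbalance into adjustment applies to propensity score variables, and prior use is not one of them. Section 9.7 also compares baseline characteristics by standardised difference, but does not name prior use among them.

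**Working it through.** **The plan's own figure.** Section 9.5 states: "We expect the study to include a minimum of 5,000 patients per arm, a conservative estimate". It reports that "approximately 200,000 patients per year with COPD were diagnosed" and that "the use of LAMA and ICS/LABA was 26 to 37%, respectively". So 200,000 × 0.26 = 52,000 and 200,000 × 0.37 = 74,000 users per year, and 5,000 is 9.6% and 6.8% of these. The total of 2 × 5,000 = 10,000 agrees with the abstract and 9.1. This is a feasibility figure: no alpha, power, effect size or SD is given, so there is no power calculation to reproduce.

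**Inputs.**
- From the documents: n = 5,000 per arm (9.5); 1:1 matching (9.7.1.1, "PS matching will be done in a 1:1 ratio using the nearest-neighbor algorithm"); 95% intervals (abstract and 9.7); balance tolerance of 0.1 (9.7.1.1).
- Assumed: outcome SD = 1, so results are in SD units; arms treated as independent; ρ, the correlation between pre-index and follow-up use that remains after the propensity score covariates, at 0.3, 0.5 and 0.7; d, the residual imbalance in pre-index use, at 0.1 SD and 0.05 SD. The documents give neither ρ nor d for this variable.

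**Precision without baseline adjustment.** SE = √(2/5,000) = 0.020 SD. The 95% half-width is 1.96 × 0.020 = 0.039 SD.

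**Bias from an unadjusted imbalance.** Bias = ρ × d. The last two columns give the chance of a significant result at the two-sided 5% level when there is no true difference, that is, P(|Z + bias/SE| > 1.96).

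| ρ | Bias at d = 0.1 | Bias/SE | False positive, d = 0.1 | False positive, d = 0.05 |
|---|---|---|---|---|
| 0.3 | 0.03 SD | 1.5 | 32% | 12% |
| 0.5 | 0.05 SD | 2.5 | 71% | 24% |
| 0.7 | 0.07 SD | 3.5 | 94% | 42% |

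At d = 0.1 the bias exceeds the half-width only if ρ > 0.0392/0.1 = 0.39. At d = 0.05 and ρ = 0.5 it is 0.025 SD, inside the half-width.

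**Effect of a larger cohort.** The 5,000 is a minimum. Four times as many patients would halve the half-width to 0.0392/2 = 0.0196 SD and lower the threshold at d = 0.1 to ρ of about 0.20. The bias itself would not change.

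**Precision gain from adjustment.** Variance falls by ρ²: 9%, 25% and 49% at ρ = 0.3, 0.5 and 0.7. At ρ = 0.5 the interval narrows by 1 − √0.75 = 13%. Without adjustment, 5,000 per arm already detects (1.96 + 0.842) × 0.020 = 0.056 SD at an assumed 80% power.

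**The case against.** The strongest reply is that the plan leaves room for this. A reader might infer from the rule about unbalanced variables that prior use is barred from every outcome model. The documents do not support that: the open clauses in 9.7.1.1 and 9.7.2 permit further covariates, the propensity score list is given as what can be achieved rather than as closed, and 9.3 and 9.7 defer detail to an SAP. The table of contents also shows a redacted entry after 9.7.2, and Annex 2 cites a 9.7.3 for sensitivity analyses that cannot be seen. So prior use is unnamed and not required in the visible text; nothing stronger can be said.

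Second, the score holds partial proxies. If exacerbation history is defined like the exacerbation outcomes in 9.3.2.1, it reflects earlier COPD admissions, emergency visits and some outpatient visits, and Charlson index and asthma add more. This stands, but does not reach all-cause admissions, other visits or total expenditure, which 9.7.2 also analyses.

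Third, 9.2 requires patients with no earlier maintenance inhaler, and COPD-related use in 9.7.2 requires COPD medication. Pre-index COPD-related values are therefore restricted by design, and ρ is probably lower for that component than for total cost.

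Fourth, the rule on unbalanced variables is written for Cox and Poisson models, and no between-group cost model is named for a covariate to enter. This is correct, and the remedy has to supply that model.

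**Conclusion.** The omission is real in every visible list, and it matters for one secondary comparison. Prior cost, visits and all-cause admissions are held in the claims, yet the visible text requires neither a balance check on them nor adjustment for them.

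The size is illustrative. A residual imbalance of 0.1 SD would bias the difference by 0.03 to 0.07 SD for ρ from 0.3 to 0.7, against a half-width of 0.039 SD. Whether that changes a conclusion depends on ρ and d, both assumed; cost skew and the pairing would alter the exact figures.

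Two stronger readings are tempting. One is that the comparison does carry a baseline difference; the documents report no imbalance, so they support only that it could. The other is that lost precision is a serious defect; with at least 5,000 per arm and no stated power target, that cannot be shown. Bias is the main argument, because a larger cohort does not shrink it.

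**What to change.** - **Section 9.7.1.1:** add total cost (log scale), number of outpatient visits and number of hospital admissions in the 12 months before index to the propensity score and the balance table.
- **Section 9.7.2, utilisation:** name a between-group model, for example a gamma GLM with log link for cost and negative binomial for counts, with pair-robust standard errors. Include the pre-index value of the same measure whatever its standardised difference. State one outcome window: 9.3.2.2 uses one year and 9.7.2 the follow-up period.

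The cost is a few derived variables from claims already in use and some SAP wording. The downside is the look-back. Section 9.4 starts the data in January 2005, while 9.2 relies on prescription history from 2002 to 2005. These must be reconciled, and the earlier claims must hold cost and visits. Otherwise the earliest initiators would be left out of this analysis and the rest matched again for it, as 9.7.1.1 already provides for subgroups.

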7. RATIONALE AND BACKGROUND

According to the GOLD guidelines, ICS use should be limited to a small portion of COPD patients³. However, ICS are largely overprescribed in clinical practice, regardless of COPD severity and exacerbation risk⁴⁻¹⁰. Even though maintenance ICS therapy is associated with an increased risk of pneumonia, physicians do not change their current practice easily^{1,3,11}. Therefore, we need a supportive data on the proper role of ICS in treating COPD patients.

Tiotropium has been the No. 1 COPD maintenance therapy over the past 12 years in South Korea and a timely review its clinical benefit in the real world setting through cumulated data.

Spiolto Respimat® has not been accumulated enough data to be compared with ICS/LABA because its launch date in Korea was April 1st 2016.

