9.2 SETTING

The study will be conducted in a general practice setting, Korea National Health Insurance claim data & mortality data from the Bureau of Statistics, which includes computerized medical records of more than half million patients in South Korea. The maximal observation period will be from Jan 2005 to Apr 2016.

- Inclusion criteria
 - Diagnosed with COPD [**based on ICD-10 code(J43.x-44.x except J430), as the primary or within the fourth secondary diagnosis and initiated LAMA or ICS/LABA more than twice a year from Jan 1, 2005 to Apr 30 2016**].
 - Age >55 years old as of 2005 when enroll started
- Exclusion criteria
 - Prescription history with any long acting bronchodilator for maintenance therapy (the patient should be inhaler naïve) from 2002 to 2005.
 - Prescription history with ipratropium bromide
 - Prescription history with Leukotriene receptor antagonist(LTRA) or ICS
 - Prescription history of LABA/LAMA FDC
 - Patients with lung cancer, IPF, ILD or lung transplantation at the time of COPD diagnosis

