9.3 VARIABLES

Detailed definitions of variables that will be derived for statistical analyses and summaries will be included in the Statistical Analysis Plan (SAP). Variables and their description are shown on (see [Appendix Table 1](#)).

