9.3.2 Outcomes

9.3.2.1 Primary outcomes

Primary endpoint

- Recorded pneumonia based on 1)ICD-10 code (J12.x-J18.x, J69.0, J84.9, B96.0, J85.1) AND 2) CPT code of chest x-ray(71045-71048) or chest CT(71250,71260,71270,G0297) AND 3) prescription of antibiotics for pneumonia in Korean Guideline) incidence rate per year
- Frequency rate of COPD exacerbation per year
 - Moderate exacerbation: recorded as when COPD patients visited outpatient clinics with an ICD-10 code of COPD and systemic steroid medication and/or antibiotics were prescribed (within the first year after initial prescription of inhalers)
 - Severe exacerbation: when COPD patients visited the emergency room or were admitted to hospital with an ICD-10 code of COPD(*due to COPD worsening*) and were prescribed systemic steroid medication and/or antibiotics (within the first year after initial prescription of inhalers)
- Time to start triple combination therapy ICS/LABA/LAMA)
 - Time to add LAMA in patients with using ICS/LABA or, time to add ICS/LABA in patients with using LAMA before.

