9.9.2 Identifying patients with COPD

The beginning of COPD symptoms cannot be determined from the utilized data sources, whereas date of diagnosis usually can be determined. Therefore, COPD patients were determined using COPD diagnostic code and a prescription for COPD medications

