ANNEX 3. ADDITIONAL INFORMATION

Appendix Table 1. List of variables in the NHIS database

DB (number of variables)	Variable name	Details
The eligibility of the insured DB	STND_Y	Standard year for the eligibility of the insured
	PERSON_ID	Personal identification number is replaced by serial number
	SEX	Sex
	AGE_GROUP	Age group at time of diagnosed
	DTH_YM	Year and month of death
	DTH_CODE1	Level 1 (detailed) cause of death
	DTH_CODE2	Level 2 cause of death
	SIDO	Province of residence
	SGG	District of residence
	CTRB_PT_TYPE_CD	Percentile group of income level
The medical treatment DB (called Table 20) [electronic bill of medical treatment]	PERSON_ID	Personal identification number is replaced by serial number
	KEY_SEQ	Key sequence number of claim
	YKIHO_ID	Medical care institution identification number
	RECU_FR_DT	The first day of receiving treatment
	FORM_CD	Form of claimed bill
	DSBJT_CD	Medical subject code
	MAIN_SICK	Main disease code
	SUB_SICK	Sub disease code
	IN_PAT_CORS_TYPE	Route through hospitalization
	OFFC_INJ_TYPE	Type of injuries incurred while on duty

DB (number of variables)	Variable name	Details
	RECN	Days of receiving medical care
	VSCN	Days of visit hospitals or inpatient
	FST_IN_PAT_DT	First date of inpatient
	DMD_TRAMT	Amount of medical expenses based on claims
	DMD_SBRDN_AMT	Expenses paid by beneficiary based on claims
	DMD_JBRDN_AMT	Expenses paid by insurer based on claims
	DMD_CT_TOT_AMT	Total amount for CT based on claims
	DMD_MRI_TOT_AMT	Total amount for MRI based on claims
	EDEC_ADD_RT	Extra rate applied based on claims reviewed
	EDEC_TRAMT	Amount of medical expenses based on claims reviewed
	EDEC_SBRDN_AMT	Amount of expenses paid by beneficiary based on claims reviewed
	EDEC_JBRDN_AMT	Amount of expenses paid by insurer based on claims reviewed
	EDEC_CT_TOT_AMT	Total amount for CT based on claims reviewed
	EDEC_MRI_TOT_AMT	Total amount for MRI based on claims reviewed
	DMD_DRG_NO	DRG number of claim
	MPRSC_ISSUE_ADMIN_ID MPRSC_GRANT_NO	Institution identification number which issued prescriptions Prescription identification number (newly added since 2011 database)
	TOT_PRES_DD_CNT	Total days of prescription
	KEY_SEQ	Key sequence number of claim

DB (number of variables)	Variable name	Details
The medical treatment DB (called Table 30) [details of medical treatment bill]	SEQ_NO	Sequence number
	RECU_FR_DT	Date of the first treatment
	CLAUSE_CD	Code for clause
	ITEM_CD	Code for item
	DIV_TYPE_CD	Code for the type of treatment

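### Lung cancer is defined by a recorded C34 code alone, so as written one unconfirmed code counts as a case and could carry part of a pneumonia difference into this endpoint

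*Combined protocol and SAP*

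**What the plan says.** Section 9.3.2.2 gives the endpoint in one line: "Recorded incidence of lung cancer (based on ICD-10 code C34.XX". Section 9.7.2 lists it among the secondary between-group analyses: "Comparison of lung cancer incidence in COPD patients using LAMA and ICS/LABA".

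Other definitions in the protocol ask for more than a diagnosis code:

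- Pneumonia (9.3.2.1) needs an ICD-10 code "AND 2) CPT code of chest x-ray(71045-71048) or chest CT(71250,71260,71270,G0297) AND 3) prescription of antibiotics for pneumonia".
- Exacerbations (9.3.2.1) need a COPD code at a visit or admission together with a systemic steroid and/or an antibiotic.
- For cohort entry, section 9.9.2 says "COPD patients were determined using COPD diagnostic code and a prescription for COPD medications".

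The readable safeguard for lung cancer is an exclusion in section 9.2: "Patients with lung cancer, IPF, ILD or lung transplantation at the time of COPD diagnosis". Section 9.3 defers detail: "Detailed definitions of variables that will be derived for statistical analyses and summaries will be included in the Statistical Analysis Plan (SAP". No separate SAP text is available.

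**The concern.** A C34 code may be entered while cancer is only suspected and never be confirmed. If that happens here, the endpoint as written counts it. The exclusion at COPD diagnosis does not help, because such codes can appear at any time in follow-up.

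Two consequences follow:

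- If false codes are equally common in both groups, they pull a real hazard ratio towards 1.
- If some arise at pneumonia work-up, they need not be equal. Every counted pneumonia involves a chest film or CT, and section 7 starts from the position that "maintenance ICS therapy is associated with an increased risk of pneumonia". Part of a pneumonia difference could then be reported as a lung cancer difference.

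Lung cancer is rare compared with chest work-ups, so even a small share of work-ups leaving a code could be a visible share of recorded cancers.

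**Working it through.** **Nothing to reproduce.** The protocol gives no lung cancer rate, effect size or power. Its 5,000 per arm (9.5) is a feasibility floor. Every rate below is an assumption, per 1,000 patient-years.

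**Model with no true lung cancer effect.** Let L be the true lung cancer rate in both groups, P the pneumonia rate with LAMA, f the share of pneumonia work-ups leaving an unconfirmed C34 code, and H the pneumonia rate ratio, ICS/LABA to LAMA. Then

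apparent ratio = (L + f·P·H) / (L + f·P).

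| L | P | f | H | Apparent ratio |
|---|---|---|---|---|
| 8 | 30 | 1% | 1.2 | 8.36/8.30 = 1.01 |
| 4 | 60 | 1% | 1.5 | 4.9/4.6 = 1.07 |
| 8 | 60 | 5% | 1.5 | 12.5/11.0 = 1.14 |
| 4 | 60 | 5% | 1.5 | 8.5/7.0 = 1.21 |
| 4 | 60 | 10% | 1.5 | 13/10 = 1.30 |

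The first two rows bound the results at f = 1% for L from 4 to 8, P from 30 to 60 and H from 1.2 to 1.5. In the last two rows false codes make up 3/7 = 43% and 6/10 = 60% of recorded LAMA-group cancers, which is extreme.

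**When only some false codes follow pneumonia.** The 1.14 row has 3 false codes per 1,000 with LAMA, all scaling 1.5-fold. If only one third of them do, the ICS/LABA rate of false codes is 2 + 1 × 1.5 = 3.5, and the ratio is 11.5/11.0 = 1.05. With 1 false code per 1,000 in total, that rate is 0.67 + 0.33 × 1.5 = 1.17, and the ratio is 9.17/9.0 = 1.02.

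**Dilution with equal false codes and a true ratio of 0.80.**

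- L = 8, 3 false codes per 1,000: (6.4 + 3)/(8 + 3) = 0.85.
- L = 8, 1 false code per 1,000: (6.4 + 1)/(8 + 1) = 0.82.
- L = 4, 3 false codes per 1,000: (3.2 + 3)/(4 + 3) = 0.89.

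**Against sampling error.** With 5,000 per arm and an assumed mean follow-up of 4 years, each arm has 20,000 patient-years. The 1.14 row then gives 250 against 220 events. The standard error of the log ratio is √(1/250 + 1/220) = 0.092, so the 95% interval is about 0.95 to 1.36. By the Schoenfeld approximation the chance of a falsely significant excess is about 28% in that row, and about 3% to 6% when f = 1%; the nominal figure is 2.5% on that side.

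**Effect of a confirmation rule.** Assume it removes 90% of false codes and keeps 95% of true cases. The 1.14 row becomes (7.6 + 0.45)/(7.6 + 0.30) = 1.02, the 1.21 row becomes 4.25/4.10 = 1.04, and the 1.30 row becomes 4.7/4.4 = 1.07.

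**Do the protocol's own assurances cover this?** Annex 2 item 10.6 points to section 9.3.3 for control of outcome misclassification, but that section lists only matching factors. Item 6.3 points to 9.7.1, which covers matching and propensity scores, and to 9.7.3, which cannot be read. The comment under Section 12 of the checklist discounts information bias because there is a single insurer. A single insurer supports complete capture; it does not make a code accurate.

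**The case against.** A reader might infer that the plan has chosen to count any one C34 code, in main or secondary position, on any claim. It does not say so. It is silent on number, position and setting, and it sends detailed definitions to the SAP. A reader might also infer that no sensitivity analysis exists. That cannot be said either: the checklist cites section 9.7.3 for outcome validity and sensitivity analyses, and that section is not readable. Both objections stand. What remains is that the endpoint line itself is readable, and followed literally it accepts one code. Section 9.7 promises a protocol amendment only for major changes to primary endpoints, so deferral gives this endpoint little protection.

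A third tempting reading is that a bias of about 14% should be expected. The documents do not say that provisional C34 codes occur in this database, let alone how often. The 1.14 needs frequent false codes that all scale with pneumonia, whereas chest imaging for other reasons may be similar in both groups. This objection stands too, so the figures are a range under stated assumptions.

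The contrast with pneumonia can also be called unfair, since that is a primary endpoint and a simpler rule for a secondary one labelled as recorded is a legitimate choice. That is reasonable: this is a choice that can be improved, not a contradiction.

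A confirmation rule has weaknesses of its own. An inpatient main diagnosis can belong to a work-up admission, and dating a case at its earliest C34 code when a later one is required conditions on surviving and remaining under observation. The fix below allows for both.

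**Conclusion.** The point holds in a limited form. As readable, section 9.3.2.2 requires no confirmation of lung cancer, and no readable part of the protocol deals with false C34 codes during follow-up. If such codes exist they dilute a true effect, and if some arise at pneumonia work-up they move the lung cancer ratio in the direction of the pneumonia difference.

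The size is unknown. With no true effect it is negligible to small if 1% of work-ups leave a false code, and reaches about 1.14 when false codes are frequent and wholly tied to pneumonia. All of this rests on assumed rates and on pneumonia differing between groups; if pneumonia does not differ, only dilution remains. At 5,000 per arm the 1.14 case would usually not reach significance, but a larger cohort would narrow the interval around the biased value. The change is a cheap improvement to a secondary endpoint.

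**What to change.** In section 9.3.2.2, make the main definition a confirmed one. A case meets any of:

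1. C34 on at least two claims at least 30 days apart;
2. a C34 claim, including one with C34 in the field Appendix Table 1 calls "Main disease code" on an inpatient claim, supported by a lung cancer procedure or cancer-treatment code;
3. C34 as cause of death, so that rapidly fatal cases are kept.

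Date the event when the definition is met, or show in a sensitivity analysis that dating at the first C34 claim does not change the result. For death-only cases use the date of death listed in section 9.6, or the month of death if only DTH_YM is supplied. Keep the code-only definition as a sensitivity analysis. If the SAP already contains a counting rule, bring it into 9.3.2.2.

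The cost is a few sentences, a code list and some programming. Sections 9.6 and Appendix Table 1 show that disease-code position, inpatient dates, procedures, medication and cause of death are held. The downside is somewhat fewer cases, mainly true cases first coded near the end of the data in April 2016. The 30-day gap is a convention and should be stated as such.
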